4. STUDY DESIGN

This is a 12-week, multi-center, single-arm, outpatient, exploratory study with 2 study periods in subjects with T1D or T2D, respectively, using an investigational reusable insulin injection pen and a commercially available CGM device. Subjects participating in the study will follow an appropriate prescribed bolus insulin regimen suitable for their disease state using insulin lispro 100 units/mL injected via the reusable insulin injection pen. During the study, subjects will have their glucose monitored via a commercially available CGM device, which will be blinded during Study Period 1 and unblinded during Study Period 2. The main purpose of the study is to estimate missed bolus insulin doses in subjects with T1D or T2D.

4.1 Sample Size Consideration

Approximately 68 subjects may be entered (i.e., signed informed consent) in order that 50 subjects complete the study. Subjects who are entered but not administered treatment may be replaced to ensure that enough subjects may complete the study. Assuming a screen fail rate

of 15%, the expected number of subjects to be screened is 80. Up to 15 subjects may be enrolled at each investigator site.

A sample size of 50 completers (approximately 25 subjects with T1D and 25 subjects with T2D) is considered sufficient for this exploratory study.

4.2 Study Scheduled Activities

Procedure Weeks from Enrollment	Study Period 1 Blinded CGM			Study Period 2 Unblinded CGM		Early D/C	Notes
	Screening/ Enrollment V1 0W	V2 3W	V3 6W	V4 9W	End of Study V5 12W		
Visit Window	N/A	3D	3D	3D	3D	N/A	Allowable deviation +/- days or weeks from scheduled visit.
Office or home visit	X	X	X	X	X	X	
Informed consent	X						
Inclusion and exclusion criteria	X						
Demography	X						
Height and weight	X						
Medical history	X						
Current medical conditions	X						Including baseline diabetes disease characteristics
Prescribed insulin regimen	X						Currently prescribed basal and bolus insulin regimen
Concomitant medication review	X	X	X	X	X	X	
Enrollment	X						
HbA1c blood draw ^a	X		X		X	X	
Pen dispensing	X						Record pen identification for dispensed pens
Pen training and start pen	X						
Confirm pen operation		X	X	X	X		
Pen collection/return					X	X	
CGM and glucose meter training	X						
CGM and pen data download		X	X	X	X	X	
Adjust CGM alert settings				X			
Hypoglycemic Confidence Scale	X		X		X	X	

	Study Period 1 Blinded CGM			Study Period 2 Unblinded CGM			
	X		X		X		
Adult Low Blood Sugar Survey	X		X		X	X	
The Big Five Inventory	X						
Health Problem Solving Scale	X		X		X	X	
Pictorial Representation of Illness and Self Measure	X		X		X	X	
General Life Stress Scale	X		X		X	X	
AE and SAE review		X	X	X	X	X	
Product complaint review		X	X	X	X	X	

Abbreviations: AE = adverse event; CGM = continuous glucose monitoring; D = days; D/C = discontinuation; HbA1c = glycated hemoglobin; N/A = not applicable; SAE = serious adverse event; V = visit; W = week.

^a HbA1c testing will be performed by local laboratories.

5. ANALYSIS POPULATIONS (ANALYSIS SETS)

5.1 Entered Analysis Set

The entered analysis set comprises all subjects who signed informed consent.

5.2 Evaluable Analysis Set

The evaluable analysis set comprises all entered subjects with ≥ 2 -week use of unblinded CGM. All efficacy analyses will be performed on this analysis set.

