Subjects will be instructed to insert a new sensor weekly and recalibrate the CGM device throughout the study. At Visit 2 (Week 3) and Visit 3 (Week 6), subjects will have their blinded CGM data and pen data downloaded by the study site personnel.

5.1.3. Study Period 2

Following the completion of Visit 3 (Week 6) assessments, subjects will begin Study Period 2 and will be unblinded to their CGM data.

At Visit 4 (Week 9), subjects will have their unblinded CGM data and pen data downloaded by the study site personnel and any required adjustments to their CGM device alarms will be performed by the study site. Insulin adjustment recommendations will be provided by the investigator and designated staff based on the available glucose and insulin data. At Visit 5 (Week 12), subjects will complete their participation in the study, and the site will download all of the pen and CGM data since the last visit.

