5.2. Number of Subjects

Approximately 80 patients will be screened to achieve approximately 68 enrolled leading to approximately 50 evaluable subjects for Study IOQV. A minimum of 28 patients and a maximum of 40 patients each of T1D and T2D will be enrolled.

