8.1. Discontinuation from Study Treatment

8.1.1. Permanent Discontinuation from Study Treatment

Discontinuation from study treatment (i.e., the pen) for a total of >3 days would lead to permanent discontinuation from study treatment as the purpose of the study is to collect data on bolus dosing. If a subject is permanently discontinued from study treatment, they will also be discontinued from the study.

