10.2. Populations for Analyses

For purposes of analysis, the following analysis sets are defined:

Table IOQV.4. Analysis Sets

Analysis Set	Description
Entered	All participants who signed informed consent
Evaluable	All enrolled subjects with ≥ 2 -week use of unblinded CGM
Safety	All enrolled subjects with any CGM or pen usage

Abbreviation: CGM = continuous glucose monitoring.

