10.3. Statistical Analyses

10.3.1. General Statistical Considerations

Statistical analysis of this study will be the responsibility of Lilly or its designee.

Efficacy analyses will be conducted on the evaluable analysis set and safety analyses on the safety analysis set defined in [Table IOQV.4](#).

Given the exploratory nature of the study, the analyses will be primarily descriptive, using descriptive statistics (mean, standard deviation [SD], minimum, median, and maximum for continuous variables; frequency and percentage for categorical variables) or graphs (e.g., scatter plot).

Missed bolus doses and glucose time-in-range will be calculated for Weeks 3-6 for Study Period 1 (blinded CGM) and Weeks 9-12 for Study Period 2 (unblinded CGM).

Any change to the data analysis methods described in the protocol will require an amendment ONLY if it changes a principal feature of the protocol. Any other change to the data analysis methods described in the protocol, and the justification for making the change, will be described in the clinical study report (CSR). Additional exploratory analyses of the data will be conducted as deemed appropriate.

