10.3.2. Efficacy Analyses

10.3.2.1. Primary Analyses

The average number of days per month with a missed bolus dose during the last 3 weeks of Study Period 1 will be summarized. The 3 weeks of data will be adjusted to a 1-month interval, and a 95% confidence interval will be calculated.

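### The primary Weeks 3–6 estimate uses only subjects who later have two weeks of unblinded CGM, which discards usable primary data and may bias the result, plausibly low

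*SAP*

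**What the plan says.** The primary endpoint belongs to Study Period 1. Protocol 10.3.2.1 states: "The average number of days per month with a missed bolus dose during the last 3 weeks of Study Period 1 will be summarized". SAP Section 10 fixes that window as the date of Visit 2 to the date of Visit 3, under blinded CGM.

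The analysis set belongs to Study Period 2. Protocol Table IOQV.4 defines the evaluable set as "All enrolled subjects with ≥ 2 -week use of unblinded CGM". SAP 5.2 uses the same criterion: the set "comprises all entered subjects with ≥ 2 -week use of unblinded CGM. All efficacy analyses will be performed on this analysis set". The one difference is that the SAP starts from entered subjects and the Protocol from enrolled subjects.

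Both documents send every efficacy analysis to this set. Protocol 10.3.1: "Efficacy analyses will be conducted on the evaluable analysis set and safety analyses on the safety analysis set". SAP 5.2 and Section 10 say the same, with no exception for the primary endpoint. In the SAP 11.1 table list, every missed-dose table is labelled Evaluable.

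Unblinded CGM does not exist before Week 6. Protocol 5.1.3 says that, once Visit 3 is complete, "subjects will begin Study Period 2 and will be unblinded to their CGM data".

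**The concern.** Membership of the primary analysis set is decided by something observed after the primary window has closed. The primary objective concerns missed boluses under blinded CGM in subjects with type 1 or type 2 diabetes. The set answers a narrower question: missed boluses among those who went on to use unblinded CGM for at least two weeks.

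This matters because the study measures non-adherence, and staying in the study is unlikely to be independent of it. More than 3 days in total off the pen "would lead to permanent discontinuation from study treatment as the purpose of the study is to collect data on bolus dosing" (Protocol 8.1.1), and from there to discontinuation from the study. If those who leave or abandon the device miss more boluses, the primary mean is too low, and its 95% confidence interval does not reflect the error.

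The visible definition also requires no minimum amount of Week 3–6 data. A subject with sparse primary data can be in the set while one with complete primary data is out.

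**Working it through.** **1. The plan's own figures.** Protocol 10.1 gives 68 subjects and a 15% screen-failure rate: 68 / (1 − 0.15) = 80, as stated. Protocol 5.2 continues: "Approximately 80 patients will be screened to achieve approximately 68 enrolled leading to approximately 50 evaluable subjects for Study IOQV". The implied loss is 68 − 50 = 18, or 18/68 = 26.5%. No dropout rate, SD or target precision is stated, so there is no precision calculation to reproduce.

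**2. When the criterion can be met.** Unblinding at Week 6 plus 2 weeks of use gives about Week 8. The primary window closes at Week 6.

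| Subject | Week 3–6 data | In primary analysis? |
|---|---|---|
| Leaves during Week 5 | at least 2 weeks of it | No |
| Leaves, or stops CGM, at Week 7 | complete | No |
| Leaves after Week 8, before Visit 4 | complete | Yes, but has no Weeks 9–12 data |

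SAP Section 10 substitutes the early-termination date for subjects who discontinue. For a Period 1 dropout that rule cannot take effect, because the subject can never be evaluable.

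**3. Size of the shift.** Let f be the excluded share of subjects who have primary data, and D the mean in excluded subjects minus the mean in evaluable subjects (days per month). The mean over all subjects with primary data is (evaluable mean) + f × D, so the evaluable-only mean is too low by f × D. Neither dropout timing nor D is in the documents. Two timing assumptions, each with 68 enrolled and 18 lost:

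| | A: even over 12 weeks | B: even, all before Week 8 |
|---|---|---|
| Lost per week | 18/12 = 1.5 | 18/8 = 2.25 |
| Reach Week 8 (evaluable) | 68 − 12 = 56 | 68 − 18 = 50 |
| Reach Week 6 (full window) | 68 − 9 = 59 | 68 − 13.5 = 54.5 |
| Reach Week 5 (≥2 weeks of window) | 68 − 7.5 = 60.5 | 68 − 11.25 = 56.75 |
| f, full window | 3/59 = 5.1% | 4.5/54.5 = 8.3% |
| f, ≥2 weeks of window | 4.5/60.5 = 7.4% | 6.75/56.75 = 11.9% |
| Shift, D = 3.3 | 0.17–0.25 | 0.27–0.39 |
| Shift, D = 5 | 0.25–0.37 | 0.41–0.59 |
| Shift, D = 10 | 0.51–0.74 | 0.83–1.19 |
| CI width, present / corrected set | √(60.5/56) = 1.04 | √(56.75/50) = 1.07 |

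D = 0 gives no bias, and a negative D gives the same shifts upward. Scenario B matches Protocol 5.2, which calls the 50 evaluable; scenario A reads the 50 as completers (Protocol 10.1).

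**4. Check without a timing assumption.** Take 50 evaluable subjects plus k excluded subjects with primary data, so f = k/(50 + k). For k = 5, 9 and 18, f = 9.1%, 15.3% and 26.5%. With D = +2 the mean is low by 0.18, 0.31 and 0.53; with D = +4, by 0.36, 0.61 and 1.06; with D = −2 it is high by 0.18, 0.31 and 0.53. k = 18 is an upper bound, since anyone lost before Week 3 has no primary data.

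**5. Scale.** At an assumed SD of 5, the 95% half-width is 1.42 at n = 50, 1.30 at n = 59 and 1.21 at n = 68.

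**The case against.** The structure is plain in the text. The case against concerns its consequence.

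- *Direction.* The rule on days off the pen is about stopping the pen, not missing boluses. Protocol 8.1.2 lists hospitalization, procedures and pen loss as reasons for interruption, and Protocol 8.2 lists exits unrelated to adherence. A miss is an excursion with no pen record in the prior hour (Protocol 9.1.1), so someone injecting by other means would appear to miss doses. Restoring such subjects could push the estimate up for the wrong reason. This stands: low is plausible, not shown.
- *Size.* D = 5 and D = 10 have no source. The nearest figure, 3.3 days per month among the one-third self-reporting omission (Protocol 3.1), is a different measure. At D = 3.3 the shift is 0.17–0.39, against a half-width of roughly 1.3 to 1.4 at SD 5. This stands as a caution on magnitude.
- *Count.* Protocol 10.1 describes the 68 as having signed consent and allows for untreated subjects, who would have no primary data. This also stands, so 18 is uncertain.
- *One cohort serves the side-by-side display.* It does not secure this. A subject with unblinded use only in Weeks 6–8 is evaluable yet has no Period 2 window data.
- *Exploratory and disclosed.* Listing 16.2.3, the disposition table and the baseline tables will show who was excluded. They do not return the observed primary data to the estimate, and that estimate with its interval is the study's main product.
- *Partial remedy.* Requiring two weeks of window data recovers 4.5 of 12 excluded subjects in scenario A and 6.75 of 18 in B, 37.5% in each. The earliest dropouts stay out. This is correct and should be acknowledged.

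**Conclusion.** The concern holds. Both documents restrict the primary blinded-CGM analysis to subjects selected on later unblinded-CGM use, and nothing in the visible text provides another efficacy set or a sensitivity analysis. That conclusion needs no assumption.

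The size does. With 68 enrolled, 18 lost and even dropout, 5.1–11.9% of subjects with primary data are excluded, depending on when losses fall and how much window data is required. At D = 5 the mean would be low by 0.25–0.59 days per month, and at D = 10 by 0.51–1.19. The interval is about 4–7% wider than it need be. There is no bias if excluded and evaluable subjects miss doses equally often, and the bias is upward if the excluded miss fewer. The shift may be modest beside sampling error, but it is avoidable and should be corrected before analysis.

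**What to change.** In Protocol Table IOQV.4 and SAP 5.2:

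1. Define the Period 1 (primary) set as all enrolled subjects with at least 2 weeks of usable blinded CGM and pen data between Visit 2 and Visit 3, or early termination if sooner, regardless of later participation. Define usable so that days with the pen documented as out of use are not counted as missed doses.
2. Apply the matching rule between Visit 4 and Visit 5 for Period 2.
3. Keep the present evaluable set as a sensitivity analysis of the primary endpoint and for the side-by-side display. If a strictly common cohort is wanted there, use subjects who are in both period sets.
4. Use enrolled in both documents.
5. State that subjects lost before about Week 5 remain outside the primary estimate, and report their number.

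No new data are needed: CGM and pen data are already downloaded at Visits 2 and 3 and at early discontinuation. The minimum programming is a population flag and one extra table for the primary endpoint. The population labels on the subgroup, time-in-range, missed-and-suboptimal-dose and diabetes-type tables, and on the period scatterplots, would also need review. N will differ between the Period 1 and Period 2 columns. Under Protocol 10.3.1 the sponsor must decide whether this changes a principal feature and so needs an amendment; otherwise the change and its justification go in the clinical study report.

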5.3 Safety Analysis Set

The safety analysis set comprises all entered subjects with any CGM or pen usage. All safety analyses will be performed on this analysis set.

6. TREATMENT DESCRIPTIONS

Unless otherwise indicated, on the summary tables, the study periods will be identified by Period 1 (Blinded CGM) and Period 2 (Unblinded CGM) respectively, side by side in the presentation.

7. STATISTICAL ANALYSIS METHODS AND ISSUES

7.1 Statistical Methods

Given the exploratory nature of the study, the analyses will be primarily descriptive, using descriptive statistics, namely sample size (n), mean, standard deviation (SD), minimum, median, and maximum for continuous variables; frequency and percentage for categorical variables. Some data will also be presented graphically using scatter plots, for instance.

7.2 Baseline Definition

The baseline is the result collected at the screening/enrollment visit.

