10. ANALYSIS OF EFFICACY ENDPOINTS

[figure not shown]
All efficacy summaries are to be performed on the evaluable analysis set by period. The GCM and Pen data collected for Weeks 3-6 (Visits 2 and 3) for Study Period 1 (blinded CGM) and Weeks 9-12 (Visits 4 and 5) for Study Period 2 (unblinded CGM) will be used in these calculations. The inclusion of the data will be based on the dates, disregard of the times even available, of the visits, which means that the GCM and Pen data will be included for the Study Period 1 if they are in the range from the date of the Visit 2 to the date of the Visit 3, inclusive, and included for the Study Period 2 if they are in the range

from the date of the Visit 4 to the date of Visit 5, inclusive. If a subject discontinues the study, the date of Early Termination will be used instead.

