10.5 Hypoglycemic Confidence Scale (HCS)

This evaluation uses the Likert scale with ratings of not confident at all, a little confident, moderately confident, and very confident to rate a subject's response to 9 items during the evaluation (8 items for subjects without a partner and 9 for subjects with a partner). Each item will receive a score from 1 to 4 based on the subject's response. HCS score is calculated as the sum of the item scores divided by the number of items completed.

The results on the Likert scale in the four categories will be summarized by descriptive statistics using frequency and percentage. The HCS score and the change from baseline will be summarized respectively.

The change from baseline to end of the period in HCS score vs. the percent time-in-range of glucose in the period will be graphically presented by a scatterplot.

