11.2 Figures

The figures of the change from baseline for these patient-reported outcomes vs. percent time-in-range of glucose will be generated for each period.

Number	Title	Population
14.2.3.2	Scatterplot of Hypoglycemic Confidence Scale (HCS) Score vs. Percent Time-in-Range of Glucose	Evaluable
14.2.3.3	Scatterplot of Adult Low Blood Sugar Survey (ALBSS) Total Score vs. Percent Time-in-Range of Glucose	Evaluable
14.2.3.4	Scatterplot of Health Problem Solving Scale (HPSS) Total Score vs. Percent Time-in-Range of Glucose	Evaluable
14.2.3.5	Scatterplot of PRISM Self Illness Separation vs. Percent Time-in-Range of Glucose	Evaluable
14.2.3.6	Scatterplot of General Life Stress Scale (GLSS) Total Score vs. Percent Time-in-Range of Glucose	Evaluable

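### Period 2 (unblinded CGM) changes in five patient-reported outcomes are taken from Visit 1, so they include the whole blinded-period change

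*SAP*

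**What the plan says.** **Baseline.** SAP 7.2 has a single definition: "The baseline is the result collected at the screening/enrollment visit". Neither document defines a Week 6 reference value.

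**Change scores.** For the HCS, SAP 10.5 states that "The HCS score and the change from baseline will be summarized respectively", and plots "The change from baseline to end of the period in HCS score vs. the percent time-in-range of glucose in the period". SAP 10.6 to 10.9 apply the same rule to ALBSS, HPSS, PRISM (self illness separation) and GLSS. SAP 10.8 adds a shift from baseline in the PRISM illness perception category.

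**Presentation by period.** SAP 10 says: "All efficacy summaries are to be performed on the evaluable analysis set by period". SAP 6 says that, unless otherwise indicated, "the study periods will be identified by Period 1 (Blinded CGM) and Period 2 (Unblinded CGM) respectively, side by side in the presentation". SAP 11.2 says: "The figures of the change from baseline for these patient-reported outcomes vs. percent time-in-range of glucose will be generated for each period". SAP 12 gives no shell for these tables, so their columns are inferred from SAP 6 and 10. The wording on the scatterplots is explicit.

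**Timing.** The schedules in Protocol 2 and SAP 4.2 place all five instruments at Visit 1 (Week 0), Visit 3 (Week 6), Visit 5 (Week 12) and early discontinuation. Protocol 5.1.3 says: "Following the completion of Visit 3 (Week 6) assessments, subjects will begin Study Period 2 and will be unblinded to their CGM data". Visit 3 is therefore the last value before unblinding. Under SAP 10, the CGM data for Period 2 run from Visit 4 to Visit 5.

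**The concern.** The period labels invite the reader to take the two change scores as parallel: what happened under blinded CGM, and what happened under unblinded CGM. With Visit 1 as the only baseline they are nested. The second contains the first, and a change made entirely in the blinded weeks appears again under the unblinded label.

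The Period 2 scatterplots have a further mismatch. One axis is a change over all 12 weeks and both CGM conditions. The other is time-in-range from three unblinded weeks. These plots are the only visible planned analyses that set the patient-reported outcomes against glycemic control, which is the exploratory objective they serve. The value needed for a within-period change is collected at Visit 3, but the plan never forms that change.

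**Working it through.** The plan states no figure on this point, so there is none to reproduce. Write V1, V3 and V5 for a subject's score at Visits 1, 3 and 5.

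**1. The planned changes** (baseline from SAP 7.2, visits from SAP 4.2)

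- Period 1: V3 − V1, Weeks 0 to 6, blinded.
- Period 2: V5 − V1 = (V3 − V1) + (V5 − V3), Weeks 0 to 12, both conditions.

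This is an identity and needs no assumption.

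**2. Illustration** (assumed changes)

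| V3 − V1 | V5 − V3 | Planned Period 2 change, V5 − V1 |
|---|---|---|
| +0.3 | 0.0 | +0.3 |
| 0.0 | +0.3 | +0.3 |
| +0.3 | −0.3 | 0.0 |

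The first two rows give the same Period 2 value from opposite histories. In the third, a full reversal in the unblinded weeks appears as no change.

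**3. What a reader can recover**

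- Mean: if the same subjects contribute to both periods, mean(V5 − V1) − mean(V3 − V1) = mean(V5 − V3) exactly. SAP 7.4 does not impute missing scores, so this fails to the extent that the contributing subjects differ.
- SD: Var(V5 − V3) = Var(V5 − V1) + Var(V3 − V1) − 2 Cov(V5 − V1, V3 − V1). The covariance is not among the planned summaries. If both printed SDs equal s and the correlation between the two changes is c, then SD(V5 − V3) = s√(2(1 − c)), which runs from 0 (c = 1) to 2s (c = −1).
- Median, minimum and maximum do not subtract. The PRISM shift from Visit 3 to Visit 5 cannot be derived from two shifts that both start at Visit 1. The subject-level scatter of V5 − V3 is not plotted.

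**4. How different the plotted variable is**

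The documents give no variances or correlations for these scores. Assume equal variance at each visit and a correlation r of 0.5 to 0.8 between adjacent visits.

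- Compound symmetry: corr(V5 − V1, V5 − V3) = (1 − r) / (2(1 − r)) = 0.50 for every r.
- AR(1): corr(V5 − V1, V5 − V3) = √(1 + r) / 2, which is √1.5 / 2 = 0.61 at r = 0.5 and √1.8 / 2 = 0.67 at r = 0.8.

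Under these assumptions the planned Period 2 variable is materially different from the change within Period 2. These figures do not say how far any association with time-in-range is distorted, or in which direction.

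**The case against.** **No objective asks for change under unblinding.** The objective for these instruments concerns characteristics associated with short-term glycemic control, has no blinded/unblinded split, and applies only if the instruments are available for use. Protocol 10.3.4 asks only for scores at the scheduled visits. A common pre-study baseline is a valid and openly stated convention. This stands as a defence of reporting V5 − V1. It does not justify making V5 − V1 the only change shown for a period that the SAP itself labels as unblinded.

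**The information is not lost.** A reader might infer that the plan conceals what happened after unblinding. The documents do not support that. Scores are summarised as well as changes, and with complete data the mean V5 − V3 follows by subtraction. The evaluable set requires at least 2 weeks of unblinded CGM, so its members entered Period 2 and largely the same subjects should feed both periods. SAP 11.3 also lists subject-level listings for HCS, ALBSS, HPSS and PRISM (none is titled GLSS), from which changes could be rebuilt by hand. The gap is in the planned summaries and figures. No confidence interval is planned for any of these outcomes, so none is lost.

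**The layout is partly inferred.** This is true of the tables, since no shell is given. It is not true of the scatterplots.

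**V5 − V3 is no clean measure of unblinding.** This stands. The study is single-arm with a fixed order, and Protocol 5.1.3 provides for insulin adjustment recommendations at Visit 4. V5 − V1 carries the same confounding plus six blinded weeks. A change over Weeks 6-12 would still be set against time-in-range from Weeks 9-12, but that matches the Period 1 pairing of Weeks 0-6 with Weeks 3-6.

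**Conclusion.** The point holds for the change summaries, the PRISM shift and the Period 2 scatterplots of the five instruments. The nesting follows from the SAP's own baseline and visit schedule. The recoverable part is the mean of V5 − V3, if the same subjects contribute. Its SD, median, range, category shift and scatter are not recoverable from the planned summaries.

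The size of any distortion in the scatterplots is unknown. A reader might reason that half the variance of V5 − V1 comes from Period 1, so that any correlation with Period 2 time-in-range shrinks by √0.5 = 0.71. The documents do not support that figure. It needs the two period changes to be independent with equal variance, and the Period 1 change to be unrelated to Week 9-12 time-in-range. V3 enters the two changes with opposite signs. Under compound symmetry their correlation is −(1 − r) / (2(1 − r)) = −0.5, and Var(V5 − V1) = Var(V5 − V3) = 2(1 − r) in units of the visit variance, so the shrinkage disappears even if the third assumption is kept. If that assumption fails, the correlation could rise or fall. The plan in any case calls only for scatterplots here, with no correlation coefficient.

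The consequence is limited. These outputs are exploratory and descriptive. Missed doses and time-in-range are computed within each period, so the primary and secondary endpoints are unaffected. The BFI, taken only at Visit 1, is also unaffected.

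**What to change.** 1. In SAP 7.2 and 10.5 to 10.9, define the Visit 3 value as the reference for the Period 2 change. Keep Visit 1 as the reference for Period 1 and for the overall change.
2. Report V5 − V3 as the Period 2 change in Tables 14.2.3.1 to 14.2.3.5, in the PRISM shift and in the Period 2 scatterplots of SAP 11.2.
3. Keep V5 − V1 as a separate row, labelled as the overall change from Visit 1 to Week 12.
4. State that V5 − V3 describes change during the unblinded period and does not isolate an effect of unblinding, because the study is single-arm with a fixed order and insulin adjustment at Visit 4.

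**Cost.** No new data and no new visit. The extra rows are 1 for HCS, 3 for ALBSS (two domains and total), 8 for HPSS (seven subscales and total) and 1 for GLSS, which makes 13. PRISM adds rows for separation (today and goal) and a further shift table. The five Period 2 scatterplots have to be revised. The protocol text on these outcomes specifies only scores at the scheduled visits, so the change does not conflict with it.
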